3.3. Re-treatment Analysis Set

The re-treatment analysis set (RTAS) will include those subjects who entered the re-treatment period. Only data collected in the re-treatment period will be included.

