4.2.2. Secondary Endpoints

The secondary endpoints include

- *the occurrence of serious adverse events (SAE, infectious and non-infectious events will be summarized separately),*
- *the occurrence of medically important infections (ie, an infection requiring hospitalization and /or parenteral [intravenous (IV), intra-muscular (IM)] anti-infective agents).*
- Hospitalization: For any hospitalizations, the admission date, discharge date and reason for hospitalization will be collected during the study.
- Death: For any deaths, date of death and cause of death will be collected during the study.

- Nonstudy medication: nonstudy medications are coded using the WHO Drug Dictionary (2006 Q3). The Prior, Concomitant, After (PCA) flag for nonstudy medications will be derived for both parent study and extension study (only for active treatment period):
 - Prior nonstudy medications are defined as any nonstudy medications taken before the first dose of investigational product taken at the start of the study,
 - Concomitant nonstudy medications are defined as any nonstudy medications taken during the treatment period (from the first dose to the last dose of the investigational product).
 - After nonstudy medications refer to any nonstudy medications taken after the last dose of the investigational product.(not applicable for observational period)
- Exposure: the total number of doses taken and exposure time.

The above endpoints will be collected for all subjects. The following endpoints will be collected only for subjects in the active treatment period, or withdrawal/re-treatment period in the extension study:

Non-serious adverse Events (Adverse events that occur up to 30 days after the last dose of investigational product will be counted as having occurred during the treatment period) This is applied for active and retreatment periods. If an AE started in active or retreatment period and continued into withdrawal or observational period, it will be only counted in active or retreatment period, it will not be counted in withdrawal or observational period again. If an event started in withdrawal or observational period, and after 30 days of the last dose of investigational product of active period or re-treatment period, this event will not be counted.

Occurrence of withdrawals from investigational product due to adverse events;

Laboratory evaluations (ie, hematology, blood chemistry, and CRP)

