Tanner Stage Assessment for subjects <18 years of age or who have a score of <5 on 1 or more applicable domain(s). The Tanner Assessment does not need to be repeated if it was performed within 2 months before the early withdrawal visit.

Vital Signs: Temperature, blood pressure (mmHg) and pulse rate (beats/min, after sitting for at least 5 minutes);

Growth parameters: height, weight, BMI;

- Efficacy:
 - *ACR Pediatric 30, 50, 70, 90, and 100, defined as $\geq 30\%$ (and 50%, 70%, 90%, 100%, respectively) improvement from baseline in at least 3 of the 6 following variables, with no more than 1 of the remaining variables worsening by $> 30\%$:*
 - *Physician's Global Assessment (PGA) of Disease Activity on a 21-circle visual analogue scale (VAS);*
 - *Patient/Parent Global Assessment on a 21-circle VAS;*
 - *Childhood Health Assessment Questionnaire (CHAQ)*

- *Number of joints with active arthritis, defined as joints that are swollen or, in the absence of swelling, joints with limited range of motion accompanied by pain and/or tenderness;*
- *Number of joints with limited range of motion;*
- *Laboratory measure of inflammation, c-reactive protein (CRP);*

(Note: ACRPedi responses will be calculated based on parent study baseline. For subjects aged ≥ 18 years, CHAQ is missing)

- *Individual components of the ACR Pediatric Assessments;*
- *Pain Assessment on a 21-circle VAS;*
- *Duration of morning stiffness in minutes;*
- *Clinically inactive disease defined as follows per 2011 Wallace Criteria:*
 - *No joints with active arthritis (defined as joints that are swollen or, in the absence of swelling, joints with limited range of motion accompanied by pain and/or tenderness);*
 - *No fever, rash, serositis, splenomegaly, or generalized lymphadenopathy attributable to JIA;*
 - *No active uveitis;*
 - *CRP level within normal limits in the laboratory where tested or, if elevated, not attributable to JIA;*
 - *PGA of disease activity score of best possible on the scale used;*
 - *Duration of morning stiffness of ≤ 15 minutes;*
- *The Juvenile Arthritis Disease Activity Score (JADAS), using 4 components (PGA of Disease Activity, Patient/Parent Global Assessment, number of joints with active arthritis and CRP).*

- *Additional Secondary Endpoints for ERA Subjects*
 - *Overall Back Pain and Nocturnal Back Pain on a 100 mm VAS;*

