5.9. Efficacy Endpoints

Descriptive summary statistics will be provided for efficacy endpoints. For continuous endpoints, the summary statistics at each visit will include the number of observations, mean, standard deviation, median, minimum, maximum and 95% confidence interval for the mean. These statistics will be provided for the observed value and change from baseline. The mean percent change from baseline will be provided also. For categorical endpoints, the summary statistics will contain the frequency, percentage, and 95% confidence interval (CI) for the percentage.

These summaries will be performed for:

- FAS, active period data (both parent and extension studies. Baseline of parent study will be used for calculation of change from baseline). The reports will show the baseline (no baseline for ACRPedi responses), weeks 12, 24, 48, and 96 from the parent study and all visits from the extension study where data is collected.
- WAS. The reports will show all visits where data is collected.

- RTAS. Re-treatment period baseline will be used for calculation of change from baseline. The reports will show all visits where data is collected.

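### The SAP does not reconcile two baselines for ACR Pedi in the re-treatment set; as written, a subject can count as a responder before the first re-treatment dose

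*SAP*

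**What the plan says.** SAP 4.2.2 lists ACR Pedi 30 to 100 among the efficacy endpoints. The list is introduced by: "The following endpoints will be collected only for subjects in the active treatment period, or withdrawal/re-treatment period in the extension study". Response requires the stated percentage "improvement from baseline in at least 3 of the 6 following variables, with no more than 1 of the remaining variables worsening by" 30%. The note under the definition reads "ACRPedi responses will be calculated based on parent study baseline" and names no analysis set or period.

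SAP 5.9 summarises efficacy for FAS, WAS and RTAS. For FAS, "Baseline of parent study will be used for calculation of change from baseline". For RTAS, "Re-treatment period baseline will be used for calculation of change from baseline". The section assigns change and percent change from baseline to continuous endpoints. For the other kind it says: "For categorical endpoints, the summary statistics will contain the frequency, percentage, and 95% confidence interval (CI) for the percentage".

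SAP 3.3 says of RTAS: "Only data collected in the re-treatment period will be included". SAP 5.4 refers to a baseline for the re-treatment period when it tabulates RTAS characteristics. The scoring algorithm in SAP 5.16.4 speaks of baseline without saying which.

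**The concern.** The only visible sentence that names a baseline for ACR Pedi points to the parent study. The RTAS sentence in 5.9 concerns a statistic that categorical endpoints do not receive. A programmer who follows the text would score RTAS response against disease before about 96 weeks in the parent study and everything since. A programmer who takes the RTAS sentence as covering the percent changes inside ACR Pedi would produce a different table.

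The choice affects interpretation. SAP section 1 gives limited knowledge of how well re-treatment works after relapse as a reason for the amendment, and RTAS is the set that bears on it. A response percentage that may already be partly met on re-treatment day 0 does not measure response to re-treatment. The composite could also disagree with its own components, which RTAS reports as change from the re-treatment baseline.

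**Working it through.** The plan states no figure that depends on this point, so there is nothing to reproduce. The check applies the response rule to the visit before the first re-treatment dose (day 0) under each baseline. All component values are assumed, because the documents give none.

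**1. Threshold.** Improvement in a component = 100 × (baseline − current) / baseline. Suppose every component at relapse is a fraction r of its parent-baseline value.

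- Against parent baseline, improvement on day 0 is 100 × (1 − r). This reaches 30% when r ≤ 0.70, 50% when r ≤ 0.50, 70% when r ≤ 0.30 and 90% when r ≤ 0.10.
- Against re-treatment baseline, improvement on day 0 is 0% for every r, so the subject is a non-responder at all levels.

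Only 3 of the 6 components need to meet the threshold, provided no more than 1 of the others is worse by over 30%. At exactly r = 0.70 the subject responds under the definition in 4.2.2 (at least 30%) but not under the column heading in 5.16.4 (more than 30%).

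**2. One subject.** The later visit is an assumed visit on re-treatment at which disease is somewhat worse than on day 0.

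| Component | Parent baseline | Day 0 | Day 0 vs parent | Later visit | Later vs parent | Later vs day 0 |
|---|---|---|---|---|---|---|
| PGA | 5 | 3 | 40% | 3.5 | 30% | −16.7% |
| Patient/parent global | 5 | 3 | 40% | 3.5 | 30% | −16.7% |
| CHAQ | 0.875 | 0.5 | 42.9% | 0.5 | 42.9% | 0% |
| Active joints | 7 | 3 | 57.1% | 4 | 42.9% | −33.3% |
| Limited joints | 6 | 3 | 50% | 3 | 50% | 0% |
| CRP | 6 | 4 | 33.3% | 4 | 33.3% | 0% |

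For example, CHAQ on day 0 gives (0.875 − 0.5)/0.875 = 42.9%.

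- Day 0 against parent: all 6 components exceed 30%, so the subject is an ACR Pedi 30 responder with no re-treatment given.
- Later visit against parent: 4 components exceed 30% and 2 equal it, so the subject is still a responder.
- Later visit against day 0: no component improves, so the subject is a non-responder.

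**3. The opposite error.** Suppose all components relapse to 120% of the parent level and fall to 80% on re-treatment. From re-treatment baseline, improvement is (120 − 80)/120 = 33.3%, a responder. From parent baseline it is (100 − 80)/100 = 20%, a non-responder. The parent baseline can therefore overstate or understate response to re-treatment.

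**4. The alternative baseline also has a fault.** SAP 5.16.4 counts a component that is zero at both visits as 0% improvement. Assume day-0 values of PGA 3, patient global 0, CHAQ 0, active joints 2, limited joints 0 and CRP 1. Let PGA and active joints fall to 0 and the rest stay unchanged. Improvements are 100, 0, 0, 100, 0 and 0%. Only 2 components improve, fewer than the 3 required, so the subject is a non-responder despite having no active joints and the best possible PGA.

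**The case against.** The strongest reply is that the RTAS line in 5.9 was meant to govern every RTAS derivation. ACR Pedi is built from percent changes, so on that reading nobody responds on day 0. SAP 3.3, which limits RTAS to re-treatment data, also fits poorly with a parent baseline. This is possible, but the specific ACR Pedi note says otherwise and has no exception, so two statements would still give two baselines for one table. Section 1 of the SAP announces definitions of baseline, and some SAP text is removed or redacted in the copy reviewed. A set-specific rule may stand there, and no missing definition is alleged.

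Parent baseline may also be deliberate. A secondary objective is long-term benefit, and 4.2.2 ties the CHAQ responder endpoint to the parent study too. This stands for FAS. In RTAS, a parent-baseline figure describes where the subject is relative to study entry, which is a legitimate but different question.

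A reader might infer that RTAS cannot show whether control is regained. The documents do not support that. RTAS also reports the individual components, pain, morning stiffness and JADAS with change from re-treatment baseline, and clinically inactive disease needs no baseline. A reader might also infer that relapses are usually mild and the rates therefore inflated. Nothing in the documents gives severity at relapse. Protocol 6.1.5 asks for prompt assessment, but withdrawal visits become six-monthly after the first year (Protocol 6.1.2.2), and re-treatment rests on the investigator's judgment (Protocol 4.1.3.1).

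**Conclusion.** The point holds as an unreconciled conflict between SAP 4.2.2 and 5.9 for ACR Pedi in RTAS. On the literal reading, day-0 response occurs whenever relapse is sufficiently milder than disease at parent entry. The 70% threshold follows from the response definition. The subject-level values are assumed, and the number of subjects affected is unknown.

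The consequence is limited. The endpoint is secondary and descriptive, RTAS is a subset of an anticipated 100 or so subjects, and neither the primary malignancy endpoint nor the sample size is touched. The finding does not show that parent baseline is wrong in general, or that RTAS response rates will be biased in a known direction. It is still worth correcting, because the RTAS percentage cannot be read without knowing its baseline.

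**What to change.** In SAP 4.2.2 and 5.9, state the ACR Pedi baseline for each analysis set.

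- **FAS:** keep the parent-study baseline.
- **WAS:** name the baseline explicitly; 5.9 gives none for this set.
- **RTAS:** report ACR Pedi against the re-treatment baseline as the measure of response to re-treatment, and name the re-treatment assessment visit as its source. Beside it, show the parent-baseline version with the percentage already responding on day 0.

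Naming the visit matters because the protocol schedules it under the withdrawal period, while SAP 3.3 limits RTAS to re-treatment data.

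The cost is one clause, one derived baseline flag and one extra table. No new data are needed, since the re-treatment assessment visit already collects the components (Protocol 6.1.5). The re-treatment-baseline version may under-count response when several components are zero at that baseline, so it should not stand alone. Both versions should be read with clinically inactive disease and JADAS.

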5. ANALYSIS METHODS

All analyses will be performed for the overall population as well as each of the 3 JIA subtypes.

5.1. Data Analysis Intervals

As shown in the study flowchart of the protocol, the visit time and the collection time of study endpoints are regularly scheduled. However, these scheduled time points may not be followed exactly. For the purpose of reporting clinical data results and satisfying the requirements of certain statistical analysis methods, it is necessary to window the actual observation time into data analysis intervals (DAIs). Details regarding the DAIs will be provided in a separate programming specifications document.

5.2. Treatment-emergent Events

An event is defined as a treatment-emergent event if the event occurred during the active period (either parent or extension studies) or re-treatment period with onset dates between the first dose date of investigational product and within 30 days after the last dose of investigational product. If a treatment-emergent event started in active or re-treatment period and continued to withdrawal or observational period, it will be only counted in active or re-treatment period, it will not be counted in withdrawal or observational period again. If an event started in the withdrawal or observational periods, and after 30 days of the last dose of investigational product of the active period or re-treatment period, this event is not a treatment-emergent event.

5.3. Subject Disposition

The numbers (and percentages) of subjects who were enrolled, who took at least one dose of investigational product, who discontinued from the parent study and who completed the parent study will be summarized from FAS. The number who completed the parent study will be further broken down into the number who did and did not continue into the extension study. The numbers (and percentages) of subjects who discontinued from the extension and who completed the extension will be summarized. This will be done separately for all subjects in the extension, for all subjects who began the extension in the active treatment period, withdrawal/re-treatment period, and for subjects who began the extension in the observational period. For those subjects who began in the active treatment period, the numbers who entered withdrawal/re-treatment period, who switched to the observational period, and reason for switching, will also be tabulated. In addition, the proportion of subjects who discontinued from the extension study for any reason and for each specific reason will be tabulated. The number and percentage of subjects who completed each year of the study may be provided.

5.4. Demography and Baseline Characteristics

Demographic, baseline characteristics (eg, subtype of JIA) and baseline disease characteristics (physician global assessment, patient/parent global assessment, Number of joints with LOM, Number of painful joints, Number of swollen joints, Pain assessment, Morning stiffness, CRP, CHAQ and HAQ. Additionally, Tender entheses score, Overall back pain VAS, Nocturnal back pain VAS, Modified Schober's test for ERA subtype; BSA of psoriasis, Physician's Global Assessment of Psoriasis for PsA subtype) data will be summarized. For continuous variables such as age, height, weight, the descriptive statistics will include the number of patients, mean, median, standard deviation, minimum, and maximum. For dichotomous variables such as sex and nominal variables such as race and ethnicity, the descriptive statistics will include the total number of patients, the count and percentage in each category. Baseline and demographic data will be summarized for subjects entered extension study (both parent study and extension study baselines), Withdrawal Analysis Set

(WAS, withdrawal period baseline), and Re-treatment Analysis Set (RTAS, retreatment period baseline).

5.5. Malignancies, SAE and Medically Important Infections

The malignancies, serious adverse events and medically important infections will be summarized using the frequency and percentage of subjects reporting events. The adjusted rate per 100 subject-years of exposure to etanercept (defined as # of events/total exposure*100) will be summarized also.

The incidence of malignancies may be compared to external data sources to generate standardized incidence ratios (SIRs) to aid interpretation.

In addition to showing cumulative rates over the entire study period (including both parent study and extension), incidences of subjects with malignancies, serious adverse events and medically important infections as well as exposure-adjusted rates will also be categorized by year for each year from 1 through 10.

These summaries and analyses will be performed for:

- FAS, all events in all periods;
- FAS, treatment-emergent events in the on-drug period (active and retreatment periods together).

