All adverse events (serious and non-serious), including infections, medically important infections, injection site reactions, and malignancy must be recorded on the CRF from the time the informed consent is signed through the duration of the withdrawal/re-treatment period. All adverse events will be collected for the duration of the withdrawal/re-treatment period and for 30 days after the last dose of investigational product for those subjects who are in either the active treatment period or the re-treatment period at Month 96.

For subjects entering directly into the withdrawal/re-treatment period at the baseline visit of study B1801023, events reported as ongoing at the final study 0881A1-3338 visit as well as events starting between the final study 0881A1-3338 visit and baseline visit of study B1801023 must also be recorded on the appropriate CRF.

For subjects in the observational period:

All serious adverse events (including serious infections), malignancy and medically important infections must be recorded on the CRF from the time the informed consent is signed or when the subject enters the observational period through the Month 96 visit.

For subjects entering into the observational period at the baseline visit of study B1801023, events reported as ongoing at the final study 0881A1-3338 visit as well as events starting between the final study 0881A1-3338 visit and baseline visit of study B1801023 must also be recorded on the appropriate CRF.

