1. INTRODUCTION

[Note: In this document, any text taken directly from the protocol is italicized.]

The purpose of this document is to provide further details about the statistical analysis methods specified in the study protocol B1801023. *Protocol B1801023 is an 8-year extension study designed to further characterize the long-term safety profile, malignancy and other serious adverse events, and clinical benefit for those pediatric subjects who received at least one dose of etanercept and completed 96 weeks of investigational product and/or follow-up in study 0881A1-3338-WW (B1801014). The previous study was designed to assess the clinical benefit and the long-term safety of etanercept for 2 years (96 weeks) in pediatric subjects with extended oligoarticular juvenile idiopathic arthritis, enthesitis-related arthritis (ERA), or psoriatic arthritis (PsA).*

Based on the lack of information regarding when treatment with etanercept should be discontinued and the success of re-treatment if relapse occurs, this protocol is being amended to also explore clinical benefit and physical function after withdrawal of etanercept and after disease relapse occurs.

A brief description of the study objectives and the study design are given in [Section 2](#). Subsequent sections include the definitions of baseline, efficacy and safety endpoints, and analysis populations followed by details about statistical methods. Any major deviations from the methods specified in this document and the protocol must be discussed in the clinical study report.

In order to evaluate overall safety in the most meaningful way, data from the 8 year extension study should not be analyzed independent of the data collected during the preceding 2 year parent study. Therefore, most of the safety analyses will be based on the combined data from the parent study and the subsequent extension. The resulting data summaries and analyses will cover the entire period of up to 10 years. In some cases, in order to fully address the entire etanercept experience, data from subjects who were in the parent study but were never enrolled in the extension study will be included in determining overall rates. Details will be provided in the following sections.

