5.11. Exposure

The exposure time (years) to etanercept will be calculated for each subject each period using (the last dose date – the first dose date + 1)/365.25. If the gap is less than 28 days between two etanercept treatment periods, the cumulative exposure will include the gap. Otherwise, the gap will be excluded from the cumulative exposure. Descriptive statistics will be provided to summarize the exposure time for:

- FAS, on-drug period (active and re-treatment periods together);
- FAS, all periods (includes commercial etanercept in withdrawal and observational periods).

The total number of doses of investigational product taken will be summarized for FAS (active and re-treatment periods together).

A table showing the number of subjects taking investigational product for 1 year, 2 years and so on through 10 years may be provided for FAS (active and re-treatment periods together).

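### The all-periods event rates in SAP 5.5 count events from all follow-up time but divide by etanercept exposure only

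*SAP*

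**What the plan says.** SAP 5.5 covers malignancy, which is the primary endpoint, together with serious adverse events and medically important infections. Besides frequency and percentage it specifies a rate: "The adjusted rate per 100 subject-years of exposure to etanercept (defined as # of events/total exposure*100) will be summarized also". The summaries are to be produced for "FAS, all events in all periods" and for treatment-emergent events in the on-drug period, both cumulatively and for each of years 1 to 10. No second formula is given.

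SAP 5.11 computes exposure per period from the first and last etanercept dose dates. A gap of less than 28 days between treatment periods is kept. For longer gaps, "Otherwise, the gap will be excluded from the cumulative exposure". Two exposure summaries are listed: the on-drug period, and "FAS, all periods (includes commercial etanercept in withdrawal and observational periods").

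Follow-up for these events is wider than dosing:

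- Under Protocol 8.2, all adverse events are recorded through the withdrawal/re-treatment period. For observational subjects, serious adverse events, malignancies and medically important infections are recorded from consent or "when the subject enters the observational period through the Month 96 visit".
- Protocol 3 and SAP 2.2.1 follow every subject for 8 years and allow any anti-TNF or other biologic in the observational period.
- SAP 1 adds that in some cases "data from subjects who were in the parent study but were never enrolled in the extension study will be included in determining overall rates".

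**The concern.** An incidence rate needs its events and its time at risk to come from the same interval. In the all-periods set, a malignancy arising in the withdrawal period, or in the observational period on another biologic or on none, enters the numerator. The time in which it arose does not enter the denominator.

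Three consequences follow.

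- The all-periods rate cannot be set beside the on-drug rate or an external rate. SAP 5.5 foresees standardized incidence ratios, whose expected count needs the person-time over which the observed cases were sought.
- In the by-year tables the inflation grows as fewer subjects remain on etanercept. A constant malignancy risk could then look like an effect of time since first dose.
- The error is toward overstating risk, which is still an error when the aim is to characterise long-term safety.

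SAP 5.5 also does not say which of the two exposures in SAP 5.11 is meant by total exposure.

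**Working it through.** The plan states no rate or expected count, so there is no figure to reproduce. The size follows from the definitions.

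**General result.** Let D be the number of events, T the subject-years of follow-up and E the subject-years of etanercept exposure. The SAP rate is 100·D/E and the follow-up rate is 100·D/T. Their ratio is T/E, which is 1 only if no follow-up time is left out of exposure. If D = 0, both rates are 0.

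**From the documents.** The parent study lasts 96 weeks: P = 672/365.25 = 1.84 years. The extension lasts 96 months, or 8 years. Complete follow-up is 9.84 years per extension subject. About 100 subjects are expected.

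**Simple case.** With complete follow-up, the ratio by assumed mean exposure is:

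| Mean exposure (years) | T/E |
|---|---|
| 9.84 | 1.00 |
| 8 | 9.84/8 = 1.23 |
| 5 | 9.84/5 = 1.97 |
| 3 | 9.84/3 = 3.28 |

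**Scenario model (all inputs assumed).** There are 100 extension subjects, all treated through week 96, and k parent-only subjects with 1.84 years each on drug. The yearly study dropout hazard is d. The yearly etanercept stopping hazard is h, without restart. A share c of later off-product time is on commercial etanercept. With s the time since extension entry, integrating from 0 to 8:

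- T = 100·(P + ∫exp(−ds) ds) + k·P
- E = 100·(P + ∫exp(−ds)·[exp(−hs) + c·(1 − exp(−hs))] ds) + k·P

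Middle case, k = 40, d = 0.05, h = 0.20. The two integrals needed are ∫exp(−0.05s) ds = 6.594 and ∫exp(−0.25s) ds = 3.459.

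- T = 100·(1.84 + 6.594) + 40·1.84 = 917
- c = 0: E = 100·(1.84 + 3.459) + 40·1.84 = 603, so T/E = 1.52
- c = 0.5: the exposure integral is (3.459 + 6.594)/2 = 5.026, so E = 760 and T/E = 1.21

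Three events would be 300/917 = 0.33 per 100 subject-years of follow-up. The SAP formula would give 300/603 = 0.50, or 300/760 = 0.39.

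Over the grid k = 0, 20, 40; d = 0, 0.05, 0.10; h = 0.1, 0.2, 0.3; c = 0, 0.5, the factor runs from 1.10 (k = 40, d = 0.10, h = 0.1, c = 0.5) to 2.02 (k = 0, d = 0, h = 0.3, c = 0).

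**By year.** The factor is 1 divided by the share of that year's follow-up spent on etanercept. At h = 0.20:

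| Year from first dose | c = 0 | c = 0.5 |
|---|---|---|
| 1 | 1.00 | 1.00 |
| 5 | 1.70 | 1.26 |
| 10 | 4.55 | 1.64 |

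**On-drug set.** SAP 5.2 counts events with onset "within 30 days after the last dose of investigational product", while exposure ends at the last dose. The mismatch per treatment course is (30/365.25) divided by the mean exposure: 1.6% at 5 years, 2.7% at 3 and 4.5% at 1.84.

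**The case against.** The strongest reply is that the two exposures in SAP 5.11 mirror the two sets in SAP 5.5. On the natural reading the all-periods rate uses the version with commercial etanercept, and only time off all etanercept is lost. That is probably the intent, and it makes the results with commercial use the more relevant ones. It narrows the mismatch without closing it. Subjects who do not relapse stay in the withdrawal period to Month 96, and Protocol 5.3.1 does not permit TNF inhibitors other than investigational product there. Observational subjects may take other biologics or none.

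The scenarios can also be challenged. They allow no re-treatment, although the protocol offers it. If restart and commercial use together covered 69% of later off-product time (an assumption), the middle case would fall to 1.12 and the grid's worst case to 1.19. A stopping hazard of 0.05 gives 1.13 in the middle case without commercial use. In the other direction, subjects who stopped in the parent study and enter observation directly would raise the factor, so 2.02 is not a ceiling. These points stand as limits on size.

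It can further be said that the rate is labelled as per etanercept exposure, that a nearly matched on-drug rate is reported alongside it, that no test depends on it and that the bias is conservative. All true. But the label does not tell the reader that the numerator includes events from outside that exposure, and the on-drug rate does not correct the all-periods rate or its by-year trend. With zero malignancies nothing changes for that endpoint, but serious adverse events and infections use the same formula.

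Finally, the FAS definition (SAP 3.1) and the text of Protocol 9.4.1 could not be read. The FAS definition settles who is counted. Protocol 9.4.1 might say more about all-subject rates, but SAP 5.5 states its own formula.

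**Conclusion.** The concern holds, and SAP 5.5 should be corrected. As written, the all-periods cumulative and by-year rates have a numerator and a denominator that cover different time, and this is so under either exposure in SAP 5.11. The direction needs no assumption beyond at least one event and some follow-up off etanercept.

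The size is follow-up divided by exposure, which is unknown in advance. The modelled range of 1.10 to 2.02 rests entirely on assumed stopping, dropout and commercial-use rates, excludes restart and should be read as illustration. The by-year distortion can be larger than the cumulative one. Frequencies and percentages are unaffected, and the on-drug rate carries only the small 30-day mismatch.

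**What to change.** In SAP 5.5, name the denominator for each set.

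- **All events in all periods:** number of events / total subject-years of follow-up × 100, with follow-up from the first etanercept dose in the parent study to last contact or death. Use the same person-time for the by-year rates and for the expected count in any standardized incidence ratio. If time stops at the first malignancy, count first malignancies only.
- **Treatment-emergent, on-drug:** keep etanercept exposure in the active and re-treatment periods, and add up to 30 days after each last dose to match SAP 5.2.
- **Optional:** show the off-etanercept rate on its own line, so that pooling with off-drug time does not hide a difference.

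The cost is SAP wording and one derived variable. Dose dates and visit or telephone contacts already exist in the study, and SAP 4.2.2 provides for deaths: "For any deaths, date of death and cause of death will be collected during the study". For parent-only subjects, last-contact dates would have to come from the parent-study database, which these documents do not describe. Some reported rates will be lower, and the two sets will need differently labelled denominators.
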